**LIST OF ABBREVIATIONS AND RELEVANT DEFINITIONS**

2D	2-dimensional
3D	3-dimensional
BT	Brachytherapy
CRF	Case Record Form
CTV	Clinical Target Volume
DCE-MRI	Dynamic Contrast Enhanced – Magnetic Resonance Imaging
DWI	Diffusion Weighted Imaging
EBRT	External Beam Radiotherapy
EORTC	European Organisation for Research and Treatment of Cancer
ESTRO	European Society for Therapeutic Radiology and Oncology
FIGO	The International Federation of Gynaecology and Obstetrics
MRI	Magnetic Resonance Imaging
OAR	Organs at Risk
PDR	Pulsed Dose Rate
HDR	High Dose Rate
PET-CT	Positron Emission Tomography – Computed Tomography
SUV	Standard Uptake Value
T/M	Tumour Muscle Ratio
MREC	Medical research ethics committee

**SUMMARY**

Title of the study	Quantitative MR Imaging in Locally Advanced Cervical Cancer
Name of study coordinators	[name], Aarhus University Hospital [name], Netherlands Cancer Institute
Objectives	
Primary: To evaluate the sensitivity and specificity of dynamic contrast enhanced (DCE-MRI) to identify patients who have increased risk of disease recurrence (local, nodal, systemic) after radio-chemotherapy of cervix cancer.
 
Secondary: To apply radiomics for identification of patients who have increased risk of disease recurrence (local, nodal, systemic) after radio-chemotherapy of cervix cancer. Radiomics analysis will include features from DCE-MRI, DWI and quantitative T2 imaging.
 
Secondary: To correlate MR imaging parameters with biomarkers based on pathology (immunohistochemistry, genomic analysis), in a subgroup of patients
 
Secondary: To evaluate the implementation of quantitative imaging in a multicentre setting.

Rationale	
Hypoxic tumour cells within the primary tumour have shown prognostic importance for local and metastatic disease control in several cancer sites. Radioresistant hypoxic cells diminish the rate of local control, and the hypoxia driven increase in metastatic potential of the tumour and lowers the rate of distant disease control. DCE MR imaging has been used to quantify the extent of poor perfusion regions within cervical tumours and it has been shown to be a surrogate of hypoxia. Furthermore, a number of studies have demonstrated that DCE MR is predictive of disease failure in cervix cancer.
 
The EMBRACE II study will implement an imaging sub-study, which will evaluate the value of quantitative MR imaging to identify patients at increased risk of disease recurrence (local, nodal and systemic).

Methodology	
Patients will undergo MRI before initiation of external beam radiotherapy. The sequences include T1W and T2W sequences as well as DWI and DCE-MRI with contrast administration. Kinetic modelling will be applied in DCE-MRI images to assess quantitative kinetic parameters in the gross tumour volume related to blood volume, interstitial

**Quantitative MR imaging in locally advanced cervix cancer**

	
volume, flow and permeability. It will be tested whether different thresholds of haemodynamic parameters can predict disease free survival.
 
Extra quantitative MR sequences can be added (optional) when the patient is MR scanned for brachytherapy treatment planning. This will allow for longitudinal evaluation of treatment response and correlation to outcome (disease free survival).

Number of patients	
At least 8 centres in the EMBRACE II consortium will offer EMBRACE II patients the possibility to participate in the imaging study. Assuming that 70% of the patients will accept participation and that 8 centres each accrue 10-20 patients, there will be a total accrual of around 80 patients per year amounting to 320 patients over the 4-year study period.

Major inclusion criteria	
 
• Patients included in the EMBRACE study (see inclusion criteria in the EMBRACE protocol)
 
• Patients without previous record of allergic reaction to infusion of protocol related contrast media (Gadolinium-based)
 
• Patients with sufficient kidney function according to local regulations
 
• Patient informed consent
 

Major exclusion criteria	
 
• According to EMBRACE II protocol
 
• Patients with active infection or severe medical condition
 

Study design	Registration study
Study duration	4 years
Hypothesis	
It is hypothesised that low perfusion in the primary tumour - as determined from DCE-MRI - is a risk factor for persistent and recurrent disease (local, nodal and systemic):
 
All patients:            Current retroEMBRACE 3/5y cancer specific survival: 81/74%            Hypothesis 3y disease free survival:                - Well perfused 89%                - Poorly perfused: 73%
 
N+ or stage III+IV:            Current retroEMBRACE 3/5y cancer specific survival: 69/57%            Hypothesis 3y disease free survival:                - Well perfused: 81%

	- Poorly perfused: 57%
Safety	For the standard DCE-MRI exam, 0.1mmol/kg of the contrast agent Dotarem (Gadoteric Acid, concentration 0.5M) is administered i.v. where minor patient discomfort may occur
Quality of Life	Not applicable
Pharmakinetics (PK)	Not applicable
Translational research (TR)	Not applicable

## 1. INTRODUCTION AND RATIONALE

Radiotherapy is an important treatment modality in the management of cancers of the uterine cervix. About half of patients with cervical cancer receive definitive radiotherapy in the course of their disease. Radiotherapy is most often administered as a combination of external beam radiotherapy (EBRT) and brachytherapy (BT). In the late 90's a major breakthrough in cervical cancer radiotherapy took place with the introduction of MR image guidance of BT. By performing MR imaging before each BT implant it is possible adapt the dose given by BT to the anatomy of each individual patient taking into account not only the position of organs at risk (bladder, rectum and sigmoid) but also the tumour regression induced by the preceding EBRT and chemotherapy.

Functional imaging that reflects hypoxia, metabolism, hemodynamics and tissue structure have been applied to locally advanced cervical cancer with the goal to identify imaging markers that may predict outcome early on and improve tissue classification. DCE-MRI may be the most investigated so far for locally advanced cervical cancer. A comprehensive literature review including papers investigating the prognostic value of DCE-MRI in patients with locally advanced cervical cancer identified 20 papers from 10 research groups, with a median number of 30 patients (range 7-102 patients). A total number of 17 papers publish a positive association between pre-treatment DCE-MRI and outcome in terms of local control or disease free survival (1–17). However, not all studies present independent cohorts of patients. Three papers show no effect (18–20) The studies on cervical cancer points in the direction that DCE-MRI has the capability to identify aggressive forms of cervical cancer, and that the pre-treatment measurements may serve as, predictive markers for outcome after chemo-radiotherapy. The largest studies indicate that in particular the tumour fraction with the lowest signal enhancement is an important parameter, though the diversity in methodology is significant.

Diffusion weighted MRI (DWI-MRI) has to a lesser extent than DCE-MRI been investigated in locally advanced cervical cancer. Most studies using DWI-MRI in cervical cancer have investigated its diagnostic capabilities (21–28) all concluding high sensitivity and specificity (review by Kundu et al. (29)). The Toronto group; McVeight et al. (26) and later Gladwish et

al. (30) found prior to the onset of treatment that the highest 90th % ADC value correlated with response, similar finding was found by the group in Tianjin; Liu et al. (22). Both groups found that higher ADC value inside the tumour was predictive of poor response to treatment and suggest the higher ADC to be connected to tumour necrosis. When tumour necrosis occurs there is loss of cell membrane integrity and therefore an increase in the extracellular volume and a decrease in intracellular volume effectively increasing the ADC. Conversely, the group from London UK; Harry et al. (31) and Somoye et al. (32) showed no correlation to treatment response at the time prior to treatment. Instead the ADC at 2 weeks (and the change in ADC) into treatment was predictive of treatment response and prognostic of patient outcome. Finally, Marconi et al. (33) found a relation between minimum ADC in the tumour and both DSS and DFS.

Publication	Imaging marker	Endpoint	# patients
DCE-MRI			
Mayr (2012) (1)	FRV	LC, DSS	102
Mayr (2010) (2)	SI(10%)	LC, DSS, OS	98
Andersen (2012) (3)	nRSI(0.5min)	LRC	81
Loncaster (2002) (4)	median SI-I (Brix model)	DSS	50
Takayama (2009) (5)	$R_{down}$	TVRR	42
Semple (2009) (6)	$K^{trans}$	TVRR	20
Mayr (1998) (7)	RSI	LC	20
Mayr (1996) (8)	RSI	LC	17
Mayr (2000) (9)	RSI	LC	16
Mannelli (2010) (10)	$NE_F$	TVRR	13
Zahra (2009) (11)	$K^{trans}, k_{ep}$	TVRR	13
Gong (1999) (12)	$\Delta ME, \Delta PE$	TVRR	7
Andersen (2011) (13)	CVF ( $K^{trans}, v_e$ )	LC	81
Mayr (2009) (14)	SI(10%)	LC, DSS, OS	88
Huang (2014) (15)	SI	LC, DSS	102
Torheim (2014) (16)	texture features from GLCMs of $A_{Brix}$	PFS	81
Donaldson (2010) (17)	$E_F(25 \text{ sec})$	DFS	50
Mayr (2010) (18)	SI(10%)	No effect (for preRT alone)	62
Kim (2012) (19)	$K^{trans}, v_e$	No effect	35
Boss (2001) (20)	TTP, BAT	No effect	10
DWI-MRI			
McVeight (2008) (26)	$ADC_{pre(90\%)}$	TVRR	47
Liu (2009) (22)	Mean $ADC_{pre}$	TVRR	17
Somoye (2012) (32)	$ADC_{wk2}, \Delta ADC_{pre-wk2}$	OS, PFS	20
Harry (2008) (31)	$ADC_{wk2}, \Delta ADC_{pre-wk2}$	TVRR	20
Marconi (2016) (33)	$ADC_{min}$	DSS	66
Gladwish (2015) (30)	$ADC_{95}, nADC_{95}$	DFS	85

*Imaging marker abbreviation*

FRV: Function Risk Volume,  $R_{down}$ : the ratio of the number of down-sloped pixels to that of all selected pixels, SI:

Signal Intensity, *SI-I*: signal intensity increase over baseline, *RSI*: Relative Signal Intensity, *nRSI*: normalized Relative Signal Intensity, *EF*: Enhancing Fraction, *NEF*: Non-Enhancing Fraction.  $\Delta ME$ : change in Mean Enhancement,  $\Delta PE$ : change in Peak Enhancement, *CVF*: Cluster Volume Fraction. *TTP*: Time To Peak, *BAT*: Bolus Arrival Time, *GLCM*: Gray Level Co-occurrence Matrix, *ADC*: Apparent Diffusion Coefficient, *nADC*: ADC normalized to diffusion in urine, *ABrix*: Amplitude in the Brix model,  $K^{trans}$ : forward volume transfer constant,  $k_{ep}$ : reverse volume transfer constant.

### Endpoint abbreviation

*DSS*: Disease Specific Survival, *OS*: Overall Survival, *LC*: Local Control, *LRC*: LocoRegional Control, *TVRR*: Tumor Volume Reduction Rate, *PFS*: Progression Free Survival, *DFS*: Disease Free Survival

## 2. OBJECTIVES

*Primary:* To evaluate the sensitivity and specificity of dynamic contrast enhanced (DCE-MRI) to identify patients who have increased risk of disease recurrence (local, nodal, systemic) after radio-chemotherapy of cervix cancer.

*Secondary:* To apply radiomics for identification of patients who have increased risk of disease recurrence (local, nodal, systemic) after radio-chemotherapy of cervix cancer. Radiomics will include features from DCE-MRI, DWI and quantitative T2 imaging.

*Secondary:* To correlate functional imaging parameters with pathology, in a subgroup of patients

*Secondary:* To evaluate the implementation of quantitative imaging in a multicentre setting.

## 3. STUDY DESIGN

This is an observational prospective, non-randomized study in which patients with locally advanced cervical cancer included in the EMBRACE II study can enrol. The study will be carried out in 8-15 EMBRACE centres.

MRI will be carried out prior to radiotherapy. The details of the MRI exams will differ from standard clinical practice in the centres, but will be consistent with international guidelines for cervix MRI. The exam will include T1, T2, diffusion, and dynamic contrast-enhanced imaging. At time of brachytherapy, the treatment planning MRI will additionally include DWI and qT2. Patients will be followed up according to the EMBRACE II follow-up schedule.

## 4. STUDY POPULATION

### 4.1 Population (base)

Yearly, each EMBRACE II centre is expected to enrol 10-20 patients. The inclusion for the imaging protocol in a given centre is expected to be 70% of patients enrolled in EMBRACE II. We expect that at least 8 institutions will enrol 10 patients per year, which will result in minimum 80 patients per year, and thereby at least 320 patients within the 4-year study period. This number is sufficient to meet the required number of patients for the hypotheses in the overall patient population (sample size 196 patients – see sample size calculation below) and in the high-risk patients (sample size 248 patients – see sample size calculation below).

### 4.2 Inclusion criteria

- Patient included in the EMBRACE II study
- Patients without previous record of allergic reaction to Gadolinium-based contrast media
- Patients with sufficient kidney function according to local regulations for intravenous Gadolinium-based contrast media administration
- Patient informed consent

### 4.3 Exclusion criteria

- According to EMBRACE II protocol
- Patients with contra indications to MRI
- Patients with active infection or severe medical condition

### 4.4 Sample size calculation

It is expected to accrue at least 320 patients (section 4.1). With this sample size it is possible to identify a significant difference with a power of at least 80% in the entire cohort as well as in a subgroup analysis in high risk patients:

All patients:

Current retroEMBRACE 3/5y cancer specific survival: 81/74%

Hypothesis 3y disease free survival:

- Well perfused (50% of patients): 89%
- Poorly perfused (50% of patients): 73%

Sample size (log-rank test, 80% power 5% significance): 196 pts

N- and stage I+II:

Current retroEMBRACE 3/5y cancer specific survival: 90/87%

Hypothesis 3y disease free survival:

- Well perfused (50% of patients): 95%
- Poorly perfused (50% of patients): 85%

Sample size (log-rank test, 80% power 5% significance): 292 pts

N+ or stage III+IV:

Current retroEMBRACE 3/5y cancer specific survival: 69/57%

Hypothesis 3y disease free survival:

- Well perfused (50% of patients): 81%
- Poorly perfused (50% of patients): 57%

Sample size (log-rank test, 80% power 5% significance): 124 pts

**Background for estimations of disease free survival and differences:**

In the entire patient cohort of Halle et al, 28% difference was found in progression-free survival with 40% and 75% progression free survival in poorly and well perfused tumours, respectively.

In the entire patient cohort of Mayr et al, 20% difference was found in disease free survival (3 years) with 60% and 80% disease free survival in poorly and well perfused tumours, respectively.

Assumptions for this study: We assume a 24% difference in cancer specific survival in the high risk group (N+ or stage III+IV), which is the mean of the difference found by Halle et al and Mayr et al. The reason that the difference is assumed in a high risk group and not in the entire group, is that disease free survival is significantly higher in retroEMBRACE than in the cohorts of Halle et al and Mayr et al. The survival reported by Halle and Mayr is more similar to the retroEMBRACE survival in the high risk group. For the low risk group (N- and stage I+II), 10% difference is assumed, and for the entire cohort 17% difference which is mean of 10% and 24%. The distribution between high and low risk patients is 50%-50%. We assume a selection of perfusion cut-point which divides the cohort into 50% well perfused and 50% poorly perfused, as was also the case in the study from Halle et al. With an overall sample size calculation based on the overall population, a number of 196 patients need to be enrolled. Sample size calculations in the high risk group indicate that with a sample size of 248 patients (2x124 patients), it is furthermore possible to observe a difference in the high risk group. It is not expected, that it is possible to perform a sub-group analysis in the low risk group with a sample size of 248 patients (a subgroup analysis in the low-risk group would require 2x292=584 patients).

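### Section 4.4 uses a 50:50 high/low-risk split for the 248-patient total, but its own survival rates imply about 43% high risk, so about 290 patients would be needed

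*Protocol*

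**What the plan says.** Section 4.4 of the Protocol gives baseline survival and a sample size for three populations:

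- All patients: "Current retroEMBRACE 3/5y cancer specific survival: 81/74" (per cent); hypothesis 89% versus 73%; "Sample size (log-rank test, 80% power 5% significance): 196 pts".
- Low risk (N- and stage I+II): "Current retroEMBRACE 3/5y cancer specific survival: 90/87"; hypothesis 95% versus 85%; "Sample size (log-rank test, 80% power 5% significance): 292 pts".
- High risk (N+ or stage III+IV): "Current retroEMBRACE 3/5y cancer specific survival: 69/57"; hypothesis 81% versus 57%; "Sample size (log-rank test, 80% power 5% significance): 124 pts".

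The background paragraphs of 4.4 then set the risk mix: "The distribution between high and low risk patients is 50%-50". From this they take a total of 248 (2 x 124) for the high-risk analysis and 584 (2 x 292) for the low-risk analysis. They describe the overall effect as "for the entire cohort 17% difference which is mean of 10% and 24". Section 4.1 repeats 248 as the requirement for the high-risk hypothesis and judges an accrual of at least 320 sufficient.

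**The concern.** The survival of a whole cohort should lie close to the average of its two risk groups, weighted by their shares. The overall retroEMBRACE rates sit nearer the low-risk rates than an even split allows. The stated 17-point overall difference is also not the difference in the rates used for the 196, which is 16 points. The even split therefore underlies one sample size (248), while the rates behind another (196) do not follow from it.

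The figure at stake is 248. It is the threshold for the only subgroup analysis that the protocol claims to power. If accrual fell short of 320 and ended between 248 and about 290, the protocol as written would call the high-risk analysis adequately sized, although its own rates suggest otherwise.

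**Working it through.** **1. Reproducing the stated sample sizes.** Inputs are the 3-year hypotheses in 4.4, 80% power and 5% significance. Sidedness is not stated; two-sided reproduces the figures. Freedman's log-rank formula with equal groups:

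- HR = ln(S_well)/ln(S_poor)
- events = (1.960 + 0.842)² x [(1 + HR)/(1 - HR)]²
- N = events / (1 - mean survival), rounded up to an even number

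| Population | Rates | HR | Event fraction | N | Stated |
|---|---|---|---|---|---|
| All | 89/73 | 0.370 | 0.19 | 196 | 196 |
| Low risk | 95/85 | 0.316 | 0.10 | 292 | 292 |
| High risk | 81/57 | 0.375 | 0.31 | 124 | 124 |

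All three match, and 124/0.50 = 248 as stated.

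**2. Risk mix implied by the retroEMBRACE rates.** With high-risk share p, S_all = p x S_high + (1 - p) x S_low, so p = (S_low - S_all)/(S_low - S_high).

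- 3 years: (90 - 81)/(90 - 69) = 9/21 = 42.9%
- 5 years: (87 - 74)/(87 - 57) = 13/30 = 43.3%

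Letting each published figure move by half a point in the least favourable combination gives 38.1-47.6% (3 years) and 40.0-46.7% (5 years). Rounding alone does not reach 50%. In the other direction, an even mix would give (90 + 69)/2 = 79.5% and (87 + 57)/2 = 72%, against the stated 81% and 74%.

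**3. The overall hypothesis.** An even mix of the subgroup hypotheses is (95 + 81)/2 = 88% well perfused and (85 + 57)/2 = 71% poorly perfused, a difference of 17 points. The rates used are 89% and 73%, a difference of 16 points. Freedman's formula gives about 184 for 88/71, against 196 for 89/73.

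**4. Consequence for 248.** Patients needed to expect 124 in the high-risk group:

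- 124/0.429 gives 290 (3-year share); 124/0.433 gives 287 (5-year share)
- rounding range: about 261-326 (3 years) and 266-310 (5 years)

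High-risk power by the same formula, with HR 0.375 and event fraction 0.31:

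| Total | High-risk share | High-risk patients | Power |
|---|---|---|---|
| 248 | 50% | 124 | 80% |
| 248 | 43% | about 107 | about 74% |
| 320 | 50% | 160 | 89% |
| 320 | 43% | about 138 | about 84% |
| 320 | 38.1% | about 122 | 79.8% |

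These are expected counts. At a 43% share, the chance of enrolling at least 124 high-risk patients is about 52% with 288 patients and about 94% with 320.

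**5. Low-risk total.** 292/0.57 = about 512, against the stated 584. Both exceed 320, so the protocol's conclusion that no low-risk subgroup analysis is feasible does not change.

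**The case against.** Four counter-arguments deserve weight.

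First, a reader might take 89/73 as independent proof of a 57:43 low/high mix, since 0.57 x 95 + 0.43 x 81 and 0.57 x 85 + 0.43 x 57 return almost exactly those rates. The documents do not support that. Each hypothesis in 4.4 is the retroEMBRACE 3-year rate plus or minus half a difference: 90 ± 5, 69 ± 12, 81 ± 8. Because 89/73 is centred on 81, it can only give back the mix already implied by 81. Even the 16-versus-17 gap could be rounding, since 17 points around 81 is 89.5/72.5. What stands is that 89/73 is not the 50:50 mix and does not show the stated 17 points. Using 89/73 is also conservative, because it gives a larger N than 88/71.

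Second, 50:50 is presented as an assumption for this study, whereas the 43% is back-calculated from cancer specific survival in an earlier cohort. The protocol does not report the case mix of retroEMBRACE or say that EMBRACE II will share it. This stands: 43% cannot simply be declared the correct share. But the protocol gives no reason for a different mix and takes its baseline rates from retroEMBRACE.

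Third, a pooled survival estimate under censoring is only approximately a weighted mean, and the 3- and 5-year figures come from one cohort. This also stands. The rounding bounds do not cover this approximation, and the two time points are not independent confirmations.

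Fourth, the power statement in 4.4 is tied to 320 patients, not 248. That is correct and limits the consequence.

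**Conclusion.** Section 4.4 is internally inconsistent about the risk mix. The 248, the 584 and the 17-point difference rest on a 50:50 split. The retroEMBRACE rates imply about 43% high risk, and the 196 rests on rates centred on 81% that differ by 16 points. If the 43% share applied, the high-risk requirement would be about 287-290 rather than 248 (rounding range about 261-326), and high-risk power at 248 would be about 74%.

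A reader might infer that the high-risk analysis is underpowered as planned. At the point estimate it is not: 320 patients give about 84% power, and only at the extreme 38% share does it fall just under 80%. The margin over the requirement shrinks from 72 patients to about 30.

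The result assumes that pooled survival is close to a weighted mean, that the retroEMBRACE mix carries over, and that the test is a two-sided log-rank test with events counted at 3 years and no allowance for dropout. Severity is moderate: a relied-on figure conflicts with its own inputs, but the planned accrual still covers the requirement at the point estimate.

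**What to change.** Reconcile the split with the rates in 4.4 in one of two ways:

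- **Adopt the implied mix.** State a high-risk share of about 43% with its basis, restate 248 as about 290 in 4.1 and 4.4, restate 584 as about 512, and correct 17 points to the 16 used. Give the range (about 261-326), since its upper end exceeds 320.
- **Keep 50:50.** Justify it for EMBRACE II, then recompute the overall hypothesis as 88% versus 71% and the 196 as about 184. The 248, the 584 and the 17 points then stand.

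Either is a text correction with no change to procedures or target accrual. The first raises the stated requirement for the high-risk analysis by about 40 patients, still below 320. It would also help to monitor the observed risk mix during accrual, because the high-risk analysis depends on the number of high-risk patients rather than on the total.
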